Clinical and Radiographic Evaluation of Pulpotomy Technique for Preserving Vitality of Traumatized Anterior Permanent Immature Teeth: A Randomized Clinical Trial

Protocol submitted to the Faculty of Dentistry, Cairo University
by
[name]
Associate Professor of Pediatric Dentistry

Faculty of Dentistry
Cairo University
January 18 , 2017

I. Administrative information:

1. Title:

Clinical and Radiographic Evaluation of Pulpotomy Technique for Preserving Vitality of Traumatized Anterior Permanent Immature Teeth: A Randomized Clinical Trial

2. Protocol Registration:

To be registered on Clinicaltrial.gov

3. Protocol version:

Final version.

4. Funding:

This trial is self-funded.

5. Roles and responsibilities:

1. **[name] ([name])** Associate Professor of Pediatric Dentistry, Cairo University. Responsible for the clinical part of study, and Data monitoring.
2. **[name] ([name])** Professor of Pediatric Dentistry, National University of Singapore, responsible for the writing revision and proof reading.
3. **[name] ([name])** Associate Professor of Pediatric Dentistry, Misr University for sciences and technology. Responsible for the clinical evaluation of the cases at the evaluation intervals

II. Introduction

6-background and rationale:

Description of research question:

P: children with vital traumatized exposed immature maxillary permanent incisors

I: Pulpotomy using Biodentine

C: MTA pulpotomy

O:

	Outcome	Tool/Device	Unit
Primary Outcome	spontaneous pain, sensitivity to percussion/ palpation)	Pain questionnaire	Binary
	Swelling or sinus tract	Visual examination by the third author	Binary
	Mobility	Back of the mirror	Binary
Secondary outcome	Stage of root development	Standardized periapical	4 stages
	Presence of radiolucency	Standardized periapical	Binary

S: Randomized clinical trial

T: 18 months (Baseline, 6, 12 and 18 months)

Research question: is Biodentine used as pulpotomy material in vital traumatized exposed immature maxillary permanent central incisors more successful clinically and radiographically than MTA pulpotomy?

Justification for undertaking the trial:

The occurrence of dental trauma in permanent teeth is a common event worldwide [1]. Children and adolescents are most frequently affected, and two-thirds of all dental trauma are found among these populations [1,2], with the anterior permanent teeth being the most affected [1, 4-6].

Traumatic injuries affecting teeth may result in pulpal and periapical disease. Complicated crown fractures which involve the enamel, dentin and pulp occur in 0.9 - 13% of all dental injuries [2,3]. Vital pulp therapy (VPT) is the treatment of choice for traumatized immature teeth with pulp exposure [5,6]. VPT aims for continuation of root development, which leads to apical closure and strengthening of the root structure [7]. If the pulp vitality of a traumatized immature tooth is lost,

endodontic treatment will constitute a real challenge. It is difficult to obtain an appropriate apical seal in these teeth by using the conventional obturation methods. Furthermore, thin root canal walls make the teeth susceptible to future fractures [8].

Primary objective of pulp therapy is to maintain the integrity and health of the teeth and their supporting tissues and to preserve vitality of the tooth pulp, especially in young permanent teeth with immature roots, where the pulp is integral to continue apexogenesis. Long term retention of a permanent tooth requires a root with a favorable crown/ root ratio and dentinal walls that are thick enough to withstand normal function. therefore, pulp preservation is a primary goal for treatment of the young permanent dentition. [9]

In modern dentistry, vital pulp therapy (VPT), whenever feasible, should be considered as an effective reasonable alternative to endodontic treatment [10]. In clinical practice, VPT includes stepwise excavation, pulp capping (direct and indirect) and pulpotomy (miniature, partial and complete), based on the amount of preserved coronal pulp [11]. The main goal of these conservative methods is to maintain the normal pulp or remove contaminated pulpal tissue in order to promote the repair process [9-11]. Therefore, immature teeth eventually gain additional benefit from VPT, considering their weak structural nature [11].

Vital pulp therapy has been increasingly considered as a minimally invasive approach for the management of teeth with inflamed pulps compared to the conventional approach of root canal treatment [12,13]. Among the factors that contributed to this choice are (1) the high frequency of technically inadequate root fillings and associated apical periodontitis despite new technologies in root canal preparation and filling , (2) the numerous advantages of VPT in terms of preserving tooth structure ,maintaining possible proprioceptive defensive mechanisms of the remaining pulp, and reducing the propensity of tooth fracture, (3) comparable success rates of VPT compared to RCT over five years of follow-up [6,7] .

Traditionally Ca (OH)₂ has been used for VPT for many years [14]. Recently MTA has replaced Ca (OH)₂ due to its ability to form an apatite-like layer, its

biocompatibility and its lack of cytotoxicity [15]. MTA due to its, biocompatibility and its ability to form cementum attachment has not only been used as a root-end filling material but also has been used as in pulpotomy, apexification, direct pulp capping and as a perforation repair material but has some drawbacks like handling property, high cost, long setting time and discoloration [14].

A magical capsule to overcome the limitations of MTA raised in the dental field called (Biodentine) [15]. It is considered a calcium silicate cement that was introduced as a ‘dentine replacement’ material, comparable to MTA in terms of biocompatibility and induction of a calcific barrier [16]. It possessed additional improvement of several properties such as mixing, handling, shorter initial setting time (12 min, with reports from 6.5–45 min) and less coronal discoloration [13].

Limited clinical data were available on the use of Biodentine in VPT; recently only three clinical trials compared Biodentine to MTA as pulp capping materials for cariously exposed teeth with high success rate approaching 100% at 1-year follow-up in young patients. [16] In a case report, Biodentine was successful in pulpotomy of traumatized permanent incisors at 48 months of follow-up [17,18].

Radiographic imaging of the dentoalveolar complex has been assessed using conventional periapical radiography, the benchmark for intraoral radiographic imaging for decades. Their known limitations of image magnification, distortion, superimposition and overlap of anatomy always led to unclear and misrepresentation of structures. Although the advent of digital intraoral radiography didn’t improve these limitations, it provided a more active image manipulation than the film-based radiographs and reduced patient exposure substantially. [19, 20]

7 - Objectives and hypothesis:

The objective of this prospective randomized clinical trial is to compare the clinical and radiographic outcomes of MTA and Biodentine as vital pulp therapy materials (pulpotomy) preserving the vitality of traumatized immature anterior permanent teeth.

8-Trial Design:

Randomized clinical trial (RCT), parallel groups with 1:1 allocation ratio, Triple blinded (patient, clinical and radiographic assessor of the results and statistician)

III- Methods:

9-Study settings:

This study will be carried out on patients attending the outpatient clinic in Pediatric Dentistry department, Faculty of Dentistry, Cairo University, Egypt. the procedures will be carried out by [name] Associate Professor of Pediatric Dentistry in Pediatric Dentistry clinic. expected time duration from 2017 to 2018.

10- Eligibility criteria:

Inclusion criteria

- The patient age range 7.5-9 years.
- Noncontributory medical history
- Unilateral/ and or bilateral central incisors tooth with complicated trauma (exposure size $\geq 1\text{mm}$)
- The tooth should give positive response to cold testing
- Clinical diagnosis of reversible pulpitis without periapical rarefaction
- The tooth is restorable, mobility was within normal limits
- No signs of pulpal necrosis including sinus tract or swelling

Exclusion criteria

- Teeth with mature roots
- Signs and symptoms of irreversible pulpitis
- Non-restorable teeth
- Negative response to cold testing, the presence of sinus tract or swelling
- No pulp exposure
- Bleeding could not be controlled after full pulpotomy in 6 minutes

IV- Intervention:

Diagnosis:

1. Full history data will be collected, including personal, medical and previous dental data
2. Clinical examination using mirror and probe to assess the inclusion criteria.
3. Radiographic examination using preoperative digital periapical radiograph to assess the inclusion criteria.

4. Preoperative photograph will be taken.

Operative procedure:

Experimental group:

1. Injection of local anesthesia and rubber dam isolation.
2. Roof of the pulp chamber will be removed by a fissure diamond bur (Diatech, Heerbrug, Switzerland) and high-speed handpiece with coolant.
3. The pulps will be amputated to the orifice level using a long-shank diamond round bur.
4. Haemostasis will be achieved by gentle placement of a saline-moistened cotton pellet over amputated pulps for 5–10 min.
5. Calcium silicate-based Biodentine™ (Septodont Ltd., Saint Maur des Fausse's, France) will be mixed according to the manufacturer's instructions, radicular pulp will be covered by the material using a wet cotton pellet.
6. A self-cure glass ionomer (GC; GC Corporation, Tokyo, Japan) will be placed over the pulpotomy agent before final restoration of composite resin (Clearfil™, Kuraray, New York, USA) will be done.
7. Immediate post-operative radiograph and photograph will be taken.

Control group:

The same procedures will be carried out as the experimental group, but the pulp stumps will be covered with white mineral trioxide aggregate (MTA) ProRoot® MTA (Dentsply/ Johnson City, TN, USA) will be used as the reference material for comparison and will be prepared according to the manufacturer's instructions. A 3-mm-thick layer of MTA will be placed over the amputated pulps and will be gently adapted to the dentinal walls using a wet cotton pellet deep onto the radicular pulp. A self-cure glass ionomer (GC; GC Corporation, Tokyo, Japan) will be placed over the pulpotomy agent before final restoration of composite resin (Clearfil™, Kuraray, New York, USA) will be done.

Postoperative care:

Instructions to avoid lip biting in addition to oral hygiene measures.

Follow up:

Assess the outcomes clinically and radiographically at (baseline, 6, 12 and 18 months).

Criteria for discontinuing or modifying intervention:

In case of an unsuccessful outcome after pulpotomy, the teeth will be managed by other pulp therapy techniques.

Strategies to improve adherence to intervention:

Explanation to the parents about the importance of follow up visits in addition to treatment of other dental problems.

Concomitant care:

None needed.

12- Outcomes:

	Outcome	Tool/Device	Unit
Primary Outcome	spontaneous pain, sensitivity to percussion/ palpation)	Pain questionnaire	Binary
	Swelling or sinus tract	Visual examination by the third author	Binary
	Mobility	Back of the mirror	Binary
Secondary outcome	Stage of root development	Standardized periapical	4 stages
	Presence of radiolucency	Standardized periapical	Binary

Primary outcome:

Clinical assessment of the findings in the table will be conducted at follow up intervals (baseline, 6, 12 and 18 months)

Secondary outcome:

Radiographic assessment of stage of root development, and presence of radiolucency will be conducted through digital periapical radiographs by parallel technique using film holders. The assessments will be carried out at follow up intervals (baseline, 6, 12 and 18 months)

13- Participants timeline:

	Study period				
	Enrolment	Allocation	Post allocation		Close out
Time point	For 9 months	0	6 months	12 months	18 months
Enrolment:					
Eligibility screen	✓				
Informed consent	✓				
History taking	✓				
Clinical examination	✓				
Preoperative radiograph	✓				
Allocation		✓			
Interventions:					
Access preparation		✓			
Placement of Biodentine (experimental group)		✓			
Placement of MTA (Control group)		✓			
Final restoration		✓			
Assessment					
Periapical radiograph as baseline reference			✓	✓	✓
Clinical examination to assess pain, swelling, fistula, tooth mobility			✓	✓	✓
Periapical radiograph to assess stage of root development and presence of radiolucency			✓	✓	✓

14- Sample size calculation:

Sample size is calculated based upon the results of Alqaderi et al (2014) [21] who reported clinical success rate (primary outcome) for MTA = 90%. Since no relevant literature reported the clinical success rate of Biodentine in permanent teeth of pediatric patients, the success rate was assumed to be 50%. Using alpha level = 0.05 and β level = 0.20 (80% Power); the minimum estimated sample size will be 20 subjects per group for a total of 40 subjects. To compensate for a drop-out rate of 15%, the number is increased to 23 subjects per group for a total of 46 subjects.

Sample size calculation will be performed using IBM® SPSS® Sample Power® Release 3.0.1.

15- Recruitment:

All patients attending the outpatient clinic in pediatric dentistry department complaining from traumatized immature permanent maxillary central incisors will be screened and enrolled in the study if they meet the eligibility criteria.

16- Allocation:

Sequence generation:

Access cavity in traumatized central incisors will be assigned into experimental or control group using simple randomization 1:1 by the help of the computer software(random.org).

Allocation concealment mechanism:

Numbered opaque sealed envelopes.

Implementation:

The child will choose an envelope randomly and open it after access preparation so that the operator knows which pulpotomy agent will be used. Sequence generation will be done by the third author and the patient assignment will be done by the operator.

17- Blinding:

Patients and their parents, the assessor and the statistician will be blinded.

18- Data collection methods:

Primary outcome:

Clinical assessment of the following findings:

1. postoperative pain: through asking the child and the parent if there is pain

either continuous or intermittent

2. Swelling: through visual examination by the assessor either intraorally or extra-orally.
3. Sinus or fistula through visual examination of the gingiva by the assessor.
4. Tooth mobility: By the back of the mirror checked by the assessor to detect mobility in any direction

This assessment will be conducted every follow-up visit throughout the study period at baseline, 6, 12 and 18 months.

Secondary outcome

Radiographic assessment to detect stage of root development and presence of radiolucency through standardized periapical radiograph by parallel technique using film holder. This assessment will be conducted every follow-up visit throughout the study period at baseline, 6, 12 and 18 months.

Postoperative records will be performed by the assessor to avoid individual variability and to promote data quality.

19- Data management:

Explanation to the parents about the importance of the follow-up visits in addition to treatment of other dental problems are plans to promotes participants retention and complete the follow-up.

Also, phone calls before the dates before the next follow-up visit will be scheduled.

All findings will be documented in the examination sheet then transferred electronically to computer in secured lace sequentially.

20- statistical methods:

All data will be collected, checked, revised, tabulated and entered into the computer. Qualitative data will be presented as frequencies and percentages. Quantitative data will be presented as mean and standard deviation values. Chi-square test and Fisher's Exact test will be used for comparisons regarding qualitative data. Student's t-test will be used to compare between mean age values in the two groups. Friedman's test will be used to study the changes by time within each group. Kaplan-Meier survival curve will be constructed to calculate the mean survival estimates of the two groups. Comparison between survival times will be performed using Log rank test.

The significance level will be set at $P \leq 0.05$. Statistical analysis will be performed with IBM® SPSS® Statistics Version 20 for Windows.

21-Monitoring:

The study data and results will be monitored regularly by the assessor who will have full access to these data.

22- Harms:

No reported adverse effects for both testing pulpotomy agents. Any adverse events appear during the trial will be recorded, documented and treated.

23-Auditing:

Auditing of the study design will be done by the evidence-based committee, Faculty of Dentistry -Cairo University.

V- Ethics and dissemination:

24-Research ethics approval:

This protocol and the template informed consent form will be reviewed by the Ethics Committee of Scientific Research - Faculty of Oral and Dental Medicine - Cairo University.

25-Protocol amendments:

Any modification to the protocol which may have an impact on the conduction of the study, potential benefit of the patient or my affect patient safety including, the changes of study objectives, study design, sample size or significant administrative aspects will require a formal amendment to the protocol.

26-Consent and Assent:

Researcher will discuss the trial with legal guardian of each participating child. They will be able to have an informed discussion with the researcher after explaining the procedure in simple words. Verbal assent will be taken orally from the participating child while written consent will be taken from the legal guardian of each participating child who is willing to participate in the trial. All consent forms will be translated into Arabic.

27-confidentiality:

All study related information will be stored securely. All participants information will be stored in locked file cabinets in an area with limited access. Process and administrative forms will be identified by a coded ID (identification number) only to maintain participants confidentiality. All records that contain names or other personal identifiers will be store separately from study records identified by code number

28-Declaration of interests:

Non-financial.

29- Access to data:

All principal investigators will be given access to the data sets. All data sets will be password protected. To ensure confidentiality, data dispersed to study team members will be blinded of any identifying participants information.

30-Ancillary and post-trial care:

Full mouth treatment will be offered to all participating children in addition to postoperative care and preventive measures though regular follow up visits after the end trial.

31- Dissemination policy:

-Study results and articles will be published in related journal.

References:

4. **Witherspoon DE.** Vital pulp therapy with new materials: new directions and treatment perspectives-permanent teeth. *J Endod.* 2008;34: S25–S28.
5. **Maryam Forghani, Iman Parisay, Amir Maghsoudlou.** Apexogenesis and revascularization treatment procedures for two traumatized immature permanent maxillary incisors: a case report *Restor Dent Endod.* 2013 Aug; 38(3): 178–181.

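### Children with two injured incisors are eligible, but the plan conflicts on whether tooth or child is allocated and names no unit of analysis

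*Combined protocol and SAP*

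**What the plan says.** The combined protocol and SAP describes a trial with "parallel groups with 1:1 allocation ratio" (Section 8). The inclusion criteria in Section 10 admit "Unilateral/ and or bilateral central incisors tooth with complicated trauma". No section says whether a second injured tooth is left out, gets the same material, or is allocated on its own.

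The unit changes between sections:

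- **Tooth.** Section 16, Sequence generation: "Access cavity in traumatized central incisors will be assigned into experimental or control group using simple randomization 1:1".
- **Child.** Section 16, Implementation: "The child will choose an envelope randomly", and "the patient assignment will be done by the operator". Section 14: "the minimum estimated sample size will be 20 subjects per group", raised to 23 for dropout. Section 15: patients at the clinic "will be screened and enrolled in the study if they meet the eligibility criteria".
- **Not stated.** Section 20 lists chi-square, Fisher's exact and log-rank tests between groups. It names neither tooth nor child as the unit and gives no method for two teeth from one mouth.

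Under Section 18, postoperative pain, part of the primary outcome, is recorded by questioning the child and the parent.

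**The concern.** Two teeth in one mouth share the injury, the operator, the hygiene and the reporter of symptoms, so their outcomes are likely to be correlated. The plan as written leaves three courses open:

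1. **Each access cavity is randomised.** Some children with two study teeth then receive both materials. Pain reported by the child or parent cannot be reliably assigned to one of them.
2. **One material per child, both teeth entered as separate rows.** The tests treat correlated rows as independent, and the type I error rises above its one-tooth level.
3. **One material and one result per child.** Neither problem arises.

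A statistician could take the second or the third course and comply with Section 20. The choice could even be made after the results are known.

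**Working it through.** **The plan's own figure.** Inputs from Section 14: success 90% v 50%, alpha 0.05 (taken as two-sided), power 80%. With pooled variance and no continuity correction:

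n = [1.96 x sqrt(2 x 0.7 x 0.3) + 0.842 x sqrt(0.9 x 0.1 + 0.5 x 0.5)]^2 / 0.4^2 = (1.270 + 0.491)^2 / 0.16 = 19.4, so 20 per group.

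Then 20 x 1.15 = 23. Both figures reproduce. The calculation has no clustering term, so it fits one result per child.

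**Assumed inputs.** The documents give neither the share f of children with two study teeth nor the within-child correlation (ICC). The ranges used are f = 0.1 to 0.5 and ICC = 0.3 to 0.8. The null failure rate is 10% (Section 14's MTA rate), with 30% and 50% as sensitivity: 50% is Section 14's Biodentine assumption and 30% is the mean of the two.

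**One material per child, both teeth counted: approximation.** Design effect = 1 + [2f/(1+f)] x ICC.

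- Low end: 1 + (0.2/1.1) x 0.3 = 1.05
- High end: 1 + (1.0/1.5) x 0.8 = 1.53

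Type I error = 2 x [1 - Phi(1.96/sqrt(design effect))], about 5.6% to 11.4%. This ignores the conservatism of Fisher's test with few failures.

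**The same, by simulation.** Beta-binomial outcomes, 46 children in equal arms, 20,000 replicates per setting. Chi-square is replaced by Fisher when an expected count is below 5, and p <= 0.05 rejects. For log-rank, failures fall at random on the 6, 12 or 18-month visit, with no earlier censoring. Each range runs from ICC 0.3 to ICC 0.8.

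| Bilateral share | Chi-square/Fisher, 10% failure | Log-rank, 10% failure | Chi-square/Fisher, 30% failure |
|---|---|---|---|
| One tooth per child | 1.6% | 4.6% | 4.9% |
| 10% | 2.1-3.0% | 4.9-5.9% | 5.6-6.6% |
| 20% | 2.6-3.8% | not run | 6.2-8.0% |
| 30% | 3.5-4.9% | 5.9-8.6% | 6.6-9.3% |
| 50% | 4.4-6.9% | 6.8-11.1% | 7.8-12.0% |

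With simple randomisation of children included, the chi-square/Fisher maximum at 10% failure is 7.5%. It passes 5% only at 30-50% share with ICC 0.8, and at 30% share only marginally. Fisher was used in 87-99% of tables at that failure rate, which explains the low figures. Over 30-50% failure, chi-square/Fisher gives about 5.5-12%, against 4.9-5.4% with one tooth per child.

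**Teeth randomised separately.** Chi-square/Fisher gives 2.0-2.7% at 10% failure and 4.7-5.3% at 30-50%. Log-rank gives 4.1-4.6% and 4.8-5.3%. These are close to the one-tooth levels. Expected number of children carrying both materials: 46 x f x 0.5, from 46 x 0.1 x 0.5 = 2.3 to 46 x 0.5 x 0.5 = 11.5.

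**Power with one tooth per child.** Exact enumeration at 90% v 50%, chi-square with Fisher when an expected count is below 5: 83% at 20 per group and 88% at 23.

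**The case against.** The best defence is that the ordinary reading is 46 children in two parallel groups. The population is defined as children, Section 14 counts subjects, the child draws the envelope, and Section 20 compares mean age between the groups, which is a child-level variable. Only the access-cavity wording points clearly to the tooth. A reader might add "the teeth will be managed by other pulp therapy techniques" from the discontinuation criteria, but that is no evidence: a failed pulpotomy is managed at the tooth whatever the unit of the trial.

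The defence also holds on size. Inflation needs one material per child and both teeth counted separately, and no section says the latter. The 10% failure null fits Section 14 best, and there chi-square/Fisher shows little inflation. The 30% and 50% nulls would have MTA failing at three to five times the rate Section 14 adopts. Log-rank inflates more at 10%, but Section 20 does not tie it to the primary outcome.

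These arguments limit the size of the problem but do not remove it. A count of subjects does not say how many teeth per child enter a test, and the sentence that governs the random sequence names the cavity. Followed literally, it lets one child receive both materials.

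**Conclusion.** The point holds as a conflict over the unit of allocation together with a missing unit of analysis. A reader might infer that the planned tests are anti-conservative in this trial. The documents do not support that: it is true only if one material is given per child and both teeth are counted, which is one of three open courses.

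Under that course and the assumed ranges, type I error at 10% failure is about 2-7.5% for chi-square/Fisher and 5-11% for log-rank. The log-rank range also rests on the assumed timing of failures. At the low end (10% share, ICC 0.3) the effect is negligible, and the documents cannot say which end applies. Under separate tooth allocation the error rate is not the issue; attribution of reported pain is. The conflict itself is certain; its size is illustrative.

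**What to change.** - **Section 16:** make the child the unit of randomisation, with one envelope and one material per child, and reword the access-cavity sentence to match.
- **Section 14:** state that the 23 per group are children.
- **Section 20:** state that the primary analysis uses one result per child. Two options are equally valid:
  - a child-level result, with failure if any treated study tooth fails; this avoids assigning reported pain to one of two teeth;
  - one index tooth, chosen by a deterministic rule fixed before the envelope is opened (for example the right incisor when both are eligible), with the other eligible tooth as fallback. A fallback is needed because the envelope is opened after access preparation, while one exclusion depends on bleeding after full pulpotomy.
- **Optional sensitivity analysis:** all teeth, with a child-clustered method, if failures suffice. At 10% failure only 46 x 0.1 = 4.6 are expected among 46 index teeth, which may be too few for a stable model.

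The cost is wording in three sections; the planned 46 is unchanged. Second teeth add little to the primary comparison. Under a child-level result, children with two study teeth have a somewhat higher chance of failure, so the 83% and 88% power figures apply strictly to one tooth per child.

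### The 6-minute bleeding exclusion does not match the 5–10 minute haemostasis step, and the plan allows that exclusion to be applied after the arm is known

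*Combined protocol and SAP*

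**What the plan says.** Three parts of the protocol bear on this point.

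**Eligibility.** The last exclusion criterion in Section 10 reads "Bleeding could not be controlled after full pulpotomy in 6 minutes". Unlike the other criteria, it cannot be assessed at screening.

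**Procedure.** In the operative procedure (Section IV), step 2 removes the roof of the pulp chamber. Step 3 states "The pulps will be amputated to the orifice level using a long-shank diamond round bur". Step 4 achieves haemostasis with a "saline-moistened cotton pellet over amputated pulps for 5–10 min". Step 5 mixes and places the material. For the control arm the plan says "The same procedures will be carried out as the experimental group", with only the agent and its placement differing, so step 4 covers both arms. Step 4 does not refer back to Section 10.

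**Allocation and blinding.** Section 16 states "The child will choose an envelope randomly and open it after access preparation so that the operator knows which pulpotomy agent will be used", and adds that "the patient assignment will be done by the operator". Section 17 states "Patients and their parents, the assessor and the statistician will be blinded"; the operator is not listed.

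Section 15 enrols children who meet the eligibility criteria, and the Section 13 timeline puts the eligibility screen at enrolment, before allocation. The timeline has a row for access preparation and then rows for placing each material. It has none for amputation or haemostasis.

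**The concern.** There are two linked problems.

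First, an operator who follows step 4 to its upper end would treat a tooth that Section 10 excludes. The protocol does not say which passage takes precedence, so the membership of the trial is unclear for teeth that stop bleeding between 6 and 10 minutes.

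Second, the criterion becomes known only during the operation, at about the time the allocation is revealed. If the envelope is opened first, the person deciding whether bleeding was controlled in time already knows the arm, and has two different time limits to choose from. Exclusion after randomisation by someone who knows the allocation is a recognised threat to comparability, and allocation concealment is meant to prevent it. Nothing elsewhere in the plan closes this route. The only discontinuation rule concerns an unsuccessful outcome after pulpotomy, not a tooth found ineligible once its envelope is open.

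**Working it through.** **1. The time limits, side by side.** Inputs: 6 minutes (Section 10) and 5–10 minutes (step 4).

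| Bleeding stops at | Section 10 | Step 4 |
|---|---|---|
| 6 minutes or earlier | eligible | treated |
| after 6, up to 10 minutes | excluded | can be treated |
| after 10 minutes | excluded | outside the stated range |

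The passages disagree only in the middle row. The documents give no distribution of bleeding times, so the share of teeth in that row cannot be stated.

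**2. When the envelope is opened.** Two readings of access preparation are possible.

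- *It covers steps 2 to 4.* In favour: the timeline has no other row before placement in which amputation and haemostasis could sit, and the agent is first needed at step 5. On this reading the criterion is settled before the arm is known.
- *It covers only opening the chamber (step 2).* In favour: amputation and haemostasis are listed as later, separate steps. On this reading the arm is known before the criterion can be judged.

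No sentence decides between the two, and none requires haemostasis before the envelope is opened.

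**3. The plan's sample size.** Inputs from Section 14: success 0.90 v 0.50, alpha 0.05 (taken as two-sided), power 80%. With the normal approximation and no continuity correction:

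n = [1.96 × √(2 × 0.70 × 0.30) + 0.8416 × √(0.90 × 0.10 + 0.50 × 0.50)]² / 0.40²
= (1.270 + 0.491)² / 0.16 ≈ 19.4, rounded up to 20 per group.

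This matches the plan. The drop-out step, 20 × 1.15 = 23, also matches. The allowance is 23 − 20 = 3 per group. Neither figure is in dispute here.

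**4. Illustration of lost numbers.** This needs three assumptions that the documents do not contain: the envelope is opened early, b units per arm are then excluded, and none is replaced. It also takes 23 per arm as fixed, although simple randomisation does not guarantee that. The planned 15% drop-out is then applied, so the evaluable number per arm is (23 − b) × 0.85. Power is exact, by enumerating two binomials at 0.90 v 0.50 with two-sided p ≤ 0.05. Section 20 names both tests.

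| b per arm | evaluable per arm | n used | Fisher | chi-square (uncorrected) |
|---|---|---|---|---|
| 0 | 19.55 | 20 | 74.2% | 83.8% |
| 1 | 18.70 | 19 | 70.9% | 81.5% |
| 2 | 17.85 | 18 | 66.8% | 78.5% |
| 3 | 17.00 | 17 | 62.6% | 75.0% |

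Only the differences belong to this point. From b = 0 to b = 3 they are 74.2 − 62.6 = 11.6 points (Fisher) and 83.8 − 75.0 = 8.8 points (chi-square). Fisher's 74.2% at b = 0 reflects the choice of test, not bleeding.

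**The case against.** The best defence is that the two passages do different jobs. Section 10 sets who is in; step 4 describes how long a pellet is held. A pellet may stay on for 8 minutes over a stump that stopped bleeding at 4, and an eligibility criterion would ordinarily govern procedural text. This has force. A reader might infer that the two limits cannot both be followed, but the documents do not support that: an operator who checks at 5 to 6 minutes and excludes teeth still bleeding complies with both. What stands is that step 4 does not carry the 6-minute stop and that its upper range is inconsistent with it.

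A reader might also note that most of the 5–10 minute range lies beyond 6 minutes and infer that many teeth are affected. Interval width says nothing about how many teeth fall in it, and the number could be negligible.

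On the envelope, the defence is that the intended order is clear: eligibility first, then allocation, with the agent revealed when it is needed. That is a fair reading of intent, and the protocol does not instruct anyone to exclude after opening. But the screen at enrolment cannot settle a criterion that exists only after amputation, and the wording leaves the order open.

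Finally, a reader might infer that the comparison is biased or that the trial loses about 10 points of power. Neither follows. The steps before placement are the same in both arms, so a limit applied equally is not expected to bias the comparison. Nothing suggests that the operator would apply it unequally, or in which direction. The power loss rests on assumed events.

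**Conclusion.** The point holds as an internal inconsistency with an open procedural route, not as a demonstrated error in the results. Section 10 and step 4 treat a tooth that stops bleeding between 6 and 10 minutes differently, whenever the envelope is opened; that part is plain from the text. The second part is conditional: on one of two tenable readings of Section 16, an unblinded operator applies the last exclusion already knowing the arm.

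No bias is shown, and its size and direction are unknown. The loss of roughly 9 to 12 points of power at three unreplaced exclusions per arm is illustrative only. It is zero if exclusion precedes opening or if excluded units are replaced. Section 20 names no analysis population, but that is a separate, plan-wide matter and this conclusion does not depend on it. Label: cheap improvement.

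**What to change.** 1. **Section 10 and operative step 4:** state one haemostasis limit, the same in both arms. Suggested text: *Bleeding must be controlled within X minutes of completing amputation; the pellet is lifted and the stump checked at X minutes.* X is 6 if Section 10 is kept; the choice is clinical and belongs to the investigators.
2. **Section 16:** replace the reference to access preparation. Suggested text: *The envelope will be opened only after haemostasis is confirmed within this limit, immediately before the material is mixed. Teeth that fail are logged as screened but not randomised.*

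The cost is text edits in three places and one line in the screening log. The envelope is opened a few minutes later in the same visit, still before the agent is needed. Keeping 6 minutes may mean screening a few more teeth; choosing 10 would admit pulps that are slower to stop bleeding. The sample size does not change.
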